### **1.2 Secondary:**

- 1- To compare post-transplant recovery of innate and adaptive immune cells (CD8, CD4, CD19, NK,  $\gamma\delta$  T-cells), in addition to T-cell phenotype markers between the two arms.
- 2- To compare post-transplant recovery of T-reg and MDSCs between the two arms.
- 3- To compare progression free survival (PFS) at 2 years post-transplant

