### **2.3 Immune reconstitution after AHSCT.**

Today's AHSCTs are almost all done with G-CSF mobilized PBSC (G-PBSC), rather than bone marrow grafts based on faster engraftment, decreased risk of infections and days of hospitalization. Early hematopoietic reconstitution of white blood cells, hemoglobin and platelets occur within the first two weeks post AHSCT. However, there is a substantial delay in reconstitution of the non-granulocytic immune components. B-lymphocytes (B-cell) recover to normal numbers within 2-4 months. Natural killer cells (CD56+3- or CD16+3- NK) reached normal values within one month post-transplant. Total T-lymphocyte (T-cell) CD3+ reconstitution occurs within 2-4 months post AHSCT. All patients showed a low CD4/CD8 ratio during the first year post transplant, due both to low numbers of CD4+ cells and elevated numbers of CD8+ cells. The low number of CD4+ cells was due to a persistently low level of naive CD4+CD45RA+ cells. While a high proportion of the CD8+ cells displayed a phenotype compatible with activated T-cells (CD8+DR+) up to 10 months after AHSCT. This seems to be secondary to the intrinsic difference between CD4 versus CD8 regeneration pathways post intensive chemotherapy. CD4 regeneration post intensive chemotherapy is more dependent on thymic function, which starts to regress even in young adults. Therefore CD4 reconstitution post AHSCT is mainly dependent on expansion of mature T-cells in the graft. A clear global

suppression of T-cell proliferative, and cytokine release in response to mitogenic agents *in vitro* has been observed in the first 6-12 months post AHSCT.

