The value of immune recovery was further highlighted in a recent report that looked at immune signatures associated with improved PFS and OS for myeloma patients treated with AHSCT. In this study, MM patients underwent comprehensive immune profiling (IP) in peripheral blood and had the marrow tested for MRD before and approximately 100 days after AHSCT. It was found that higher  $\gamma\delta$  T-cell counts post-AHSCT correlated with improved 2-year PFS and OS. Furthermore, the higher CD4+ central memory (CM) cell counts post-AHSCT were associated with improved 2-year OS but not PFS. The higher  $\gamma\delta$  T-cell and CD4+ CM-cell count associations were primarily observed in MRD-negative patients post-AHSCT and in patients not receiving maintenance therapy.

Collectively these studies suggest that high ALC and low AMC on day 15 post AHSCT are markers of accelerated immune recovery, and lower immune suppression, resulting in lower risk of relapse and better long-term survival.

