### **10.2 Secondary Objectives**

For the secondary objectives, engraftment, development of any auto immune side effects, and infections will be treated as binary variables. Chi-square tests will be used to compare each of these 3 outcome variables between the two groups, respectively. A Wilcoxon signed-ranks test will be employed to test the change in absolute lymphocyte (ALC), absolute monocyte counts (AMC), immune cells (T cells CD8, CD4), natural killer cells,  $\gamma\delta$  T-cells, T-reg and MDSCs) at days 15 and 30 post AHSCT from the baseline among each group, respectively. Wilcoxon signed-ranks test will be further used to compare the change of change in ALC, AMC and immune cells between the two groups at days 15 and 30 post- AHSCT, respectively.

Generalized linear mixed models will be employed to compare the change pattern of ALC, AMC and immune cells between the two groups over the entire follow up periods. Time to relapse and overall survival will plotted using the methods of Kaplan and Meier and the log rank test will be used to compare the time to event curves between the two treatment groups.

Lastly, as an explorative objective will also be depth of anti-myeloma response as evaluated by the standard IMWG criteria, including the rate of sCR, and subsequent MRD status for the subjects in sCR.

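### Section 10.2 omits CD19 and the T-cell phenotype markers of secondary objective 1, and sets no day-specific between-arm comparison after day 30

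*Combined protocol and SAP*

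**What the plan says.** Section 1.2 sets secondary objective 1: "To compare post-transplant recovery of innate and adaptive immune cells (CD8, CD4, CD19, NK" and gamma-delta T cells), "in addition to T-cell phenotype markers between the two arms". It gives no time point. Recovery of T-reg and MDSC is a separate objective, secondary objective 2.

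Section 10.2 has three analyses of cell counts:
- Within each arm, a signed-ranks test is used to "test the change in absolute lymphocyte (ALC), absolute monocyte counts (AMC), immune cells (T cells CD8, CD4), natural killer cells", gamma-delta T cells, T-reg and MDSC, "at days 15 and 30 post AHSCT from the baseline among each group, respectively".
- Between arms, the plan is: "Wilcoxon signed-ranks test will be further used to compare the change of change in ALC, AMC and immune cells between the two groups", again at days 15 and 30.
- Generalized linear mixed models compare the pattern of change in ALC, AMC and immune cells between the arms over all of follow-up.

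Flow cytometry is scheduled after transplant at days 15, 30, 70, 100 and 180 in both arms (Sections 5.1.2 and 5.1.13). Section 5.7.2 names B cells among the phenotypes to be compared between groups.

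On timing, Section 2.3 says: "Total T-lymphocyte (T-cell) CD3+ reconstitution occurs within 2-4 months post AHSCT". It gives the same 2-4 months for B cells and within one month for NK cells. Section 2.6 supports the gamma-delta and CD4 central-memory readings with a study in which patients had "comprehensive immune profiling (IP) in peripheral blood and had the marrow tested for MRD before and approximately 100 days after AHSCT".

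**The concern.** An objective and its analysis should name the same variables. As Section 10.2 is written, an analyst who follows it would report nothing on CD19 or on any T-cell phenotype marker. B cells are the lineage behind the antibody (ELISA) half of the primary endpoint, and CD4 central-memory cells are one of the two subsets that the background cites as prognostic.

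The second gap is timing. The day-specific comparisons are made before the period in which the protocol expects adaptive cells to recover. The mixed model reaches that period, but with no stated time contrast it can show that the profiles differ without saying whether the arms differ at 2-4 months. A contrast picked after the data are seen would carry little weight. Section 10.1 compares vaccine response at days 30, 70, 100 and 180, so only day 30 is shared with the day-specific cell tests that might help to explain that response.

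**Working it through.** **1. Objective against analysis**

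| Item in secondary objective 1 | In the Section 10.2 list? | Day-specific tests | Timing given in the background |
|---|---|---|---|
| CD8 | yes | days 15, 30 | CD3+ T cells, 2-4 months (2.3) |
| CD4 | yes | days 15, 30 | CD3+ T cells, 2-4 months (2.3) |
| CD19 | no | none | B cells, 2-4 months (2.3) |
| NK | yes | days 15, 30 | within one month (2.3) |
| Gamma-delta T | yes | days 15, 30 | prognostic reading about day 100 (2.6) |
| T-cell phenotype markers | no | none | CD4 central memory, about day 100 (2.6) |

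Named cell types covered: 4 of 5, with no phenotype marker. Visits with a day-specific test: 2 of 5. Visits inside 2-4 months: days 70 (+14) and 100 (+/-10), neither of them tested by day.

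**2. The plan's own power figure.** Section 10.5 states at least 80% for a two-sided Mann-Whitney test, d = 1.36, 10 per arm, alpha 5%. With the Mann-Whitney efficiency 3/pi for Normal data, effective n per arm = 10 x 3/pi = 9.55. The noncentrality is 1.36 x sqrt(9.55/2) = 2.97 on 2 x 9.55 - 2 = 17.1 degrees of freedom, and power is 0.800. The figure reproduces. Simulating the exact test gives 0.78 (actual alpha 0.043), and 0.71 at 9 v 9. This figure is for vaccine response; the plan gives none for cell recovery.

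**3. What each analysis would detect, under assumed profiles.** Assumptions: 10 per arm, SD 1, within-subject correlation 0.3 to 0.7, largest difference d = 1.36 (borrowed from Section 10.5). A multivariate arm-by-time test over the five visits stands in for the mixed model.

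| Assumed arm difference | Mann-Whitney, days 15 and 30 | Mann-Whitney, day 100 | All-visit profile test |
|---|---|---|---|
| Only from day 70 | 4-5% | 77-79% | 80-99% |
| Growing (0.1, 0.3, 0.9, 1.36, 1.36) | 4-5%, 9% | 77-79% | 55-92% |
| Early, then fading (1.36, 1.36, 0.6, 0.2, 0) | 77-79% | 6-7% | 64-96% |

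The ranking of the day-specific tests depends wholly on the assumed profile.

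**4. Number of tests.** Now: 8 variables x 2 days = 16 between-arm tests. Adding CD19 at days 15 and 30 gives 9 x 2 = 18. Adding day 100 for the five cell types of objective 1 gives 18 + 5 = 23, before phenotype markers. If the tests were independent, the chance of at least one false positive at 5% would go from 1 - 0.95^16 = 0.56 to 1 - 0.95^23 = 0.69.

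**5. The between-arm test.** Signed ranks needs pairs. The arms are independent randomised groups, and blocks of 2 or 4 (Section 4.3) do not match individuals. The plan would also have no way to form pairs if the arms ended unequal.

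**The case against.** A reader might infer that objective 1 is tested at the wrong time. The documents do not support that.

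- The mixed model in the same section compares the arms over the whole follow-up, so CD8, CD4, NK and gamma-delta T cells are also compared at days 70 to 180.
- Days 15 and 30 have a stated basis: ALC and AMC at day 15 (Sections 2.6 and 5.7.1), and NK within one month (Section 2.3).
- The trial's hypothesis is accelerated recovery. The 2-4 months in Section 2.3 is when counts normalise after existing transplants, not when the arms would differ most. Arms may converge as both normalise.

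A reader might also take 5% against 78% as the power lost by stopping at day 30. Those figures assume no difference before day 70, borrow the vaccine-response effect size and leave out the mixed model.

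Finally, the gap may be one of wording. The list in Section 10.2 has unbalanced brackets, the later sentences say only immune cells, and Sections 5.7.2 and 6.0 intend group comparisons of flow data. CD4 central memory is named only in the background.

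All of this stands against the stronger readings. It does not supply the missing variables or a named late contrast: the only cell list in Section 10.2 leaves out CD19 and every phenotype marker. The intention elsewhere to compare B cells is a reason to complete that list.

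**Conclusion.** The point holds as a mismatch between objective and analysis, not as an error that invalidates the secondary analysis. One of five named cell types and all the phenotype markers have no named analysis in Section 10.2. No day-specific comparison or model contrast falls at days 70, 100 or 180. The between-arm test named for days 15 and 30 is a paired test applied to independent arms.

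This rests on reading immune cells, in the between-arm and mixed-model sentences, as the list given just before them. A broader reading would bring CD19 into the model but would still leave the contrast unstated. No figure for lost power is claimed, because it would depend on a recovery profile that the documents do not give. The primary comparison in Section 10.1 is not affected.

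**What to change.** In Section 10.2:

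1. Add CD19+ B cells and the named T-cell phenotype markers to the list, for both the day-specific tests and the mixed model. Section 5.7.2 does not list the markers, so name them and confirm that the flow panel measures them; include CD4 central memory if it does.
2. Pre-specify, labelled exploratory, a day-100 (+/-10) between-arm comparison of the objective 1 subsets. Use either a contrast from the planned mixed model or a Mann-Whitney test on change from baseline. State which pre-transplant draw is baseline, since Section 5.1.2 schedules flow at three. Day 100 matches the timing cited in Section 2.6 and is the last scheduled draw before Section 5.2.2 allows post-transplant myeloma therapy to start (progression excepted).
3. Keep the day 15 and 30 comparisons, including T-reg and MDSC for secondary objective 2, but compare the arms with a two-sample rank-sum test. Signed ranks remains suitable for change within an arm.

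The cost is wording and a little analysis of flow visits already scheduled. The downside is a few more uncorrected comparisons in an analysis that Section 10.5 already declares exploratory and uncorrected.

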### **1.3 Exploratory objective:**

To compare the depth of multiple myeloma (MM) response by international myeloma working group (IMWG) criteria, including analyzing minimal residual disease (MRD) status at 3 and 6 months post-transplant for those subjects who are close to achieving CR (defined as monoclonal serum protein of  $\leq 0.1$  g/dL, with negative urine protein electrophoresis) between the two arms.

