## **5.2 Post transplant Myeloma Management:**

5.2.1 All post-transplant myeloma staging and therapy will be based on local standard of clinical practice for myeloma subjects. Subjects will undergo *Euroflow-based* MRD staging if they are deemed to be close to CR (serum protein electrophoresis < 0.1 gdL, but serum immunofixation positive) based on IMWG criteria.

5.2.2 For all subjects, post-transplant myeloma specific therapy may not be started before the day 100 (+/-10) visit on this protocol. The only exception would be disease progression that occurs before day+100, in which case the subject will be taken off study.

5.2.3 Subjects on this protocol may not enroll on other treatment/interventional protocols for the first 100 (+/-10) days post-transplant. The only exception would be disease progression before day+100, in which case, the subject is off study.

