## Section 7.0 Study Parameters

Examinations and Assessments	Baseline (Screening)	Pre-Transplant (SCT)				Transplant	Post Transplant Period										Follow up Period
	Pre vaccine	Vaccine (day -19)	Day -12 to -9	Day -11 to -7	Day -6 to -4	AHSCT Hospitalization	Day + 7	Day +15	Day +30	Day +60	Day +70	Day +100 (mo. 3)	Day +130 (mo. 4)	Day +150 (mo. 5)	Day +180 (mo. 6)	Day +365 (1 yr)	Survival status (2 years)
Window Days for Study Visit 	-30 days (+/-10 days)					Day 0		+/-3	+14	+/-3	+14	+/-10	+/-7	+/-7	+/-10	+/-30	+/-30 days
Informed Consent	X																
Inclusion/Exclusion Criteria	X																
Pregnancy testing	X 																
Medical History	X																
Clinical Assessment	X 																
Data collection to assess organ function (labs) 	X																
Disease response 	X												X			X	X
Data collection for Disease Assessment													X				

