## Section 7.0 Study Parameters

Examinations and Assessments	Baseline (Screening)	Pre-Transplant (SCT)				Transplant	Post Transplant Period										Follow up Period
	Pre vaccine	Vaccine (day -19)	Day -12 to -9	Day -11 to -7	Day -6 to -4	AHSCT Hospitalization	Day + 7	Day +15	Day +30	Day +60	Day +70	Day +100 (mo. 3)	Day +130 (mo. 4)	Day +150 (mo. 5)	Day +180 (mo. 6)	Day +365 (1 yr)	Survival status (2 years)
(imaging and bone marrow)																	
Data collection for Disease assessment (blood and urine)	X											X			X	X	X
Adverse Events						X	X	X	X	X	X	X	X	X	X	X	X
Assessment for Subject/Graft Survival							X	X		X	X			X			X
Hematology (complete blood count (CBC) with differential ALC platelets)	X					X	X	X	X	X	X			X	X	X	
Randomization	X																

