## Section 7.0 Study Parameters

Examinations and Assessments	Baseline (Screening)	Pre-Transplant (SCT)				Transplant	Post Transplant Period										Follow up Period
	Pre vaccine	Vaccine (day -19)	Day -12 to -9	Day -11 to -7	Day -6 to -4	AHSCT Hospitalization	Day + 7	Day +15	Day +30	Day +60	Day +70	Day +100 (mo. 3)	Day +130 (mo. 4)	Day +150 (mo. 5)	Day +180 (mo. 6)	Day +365 (1 yr)	Survival status (2 years)
Tetanus Vaccine		X						X		X							
Group 1  / Pre G-CSF PBMC pheresis			X														
Group 1 – Post-AHSCT PBMC infusion							X										
G-CSF (both groups)				X													
Pre Stem Cell harvest / Graft Pheresis (both groups) 					X												
Immune correlative study blood draw		X	X 		X			X	X		X	X		X			

 Pre-PBMC harvest in group 1 7-10 day post vaccine only

Clinical Assessment is billed as physical exam with performance score. Data will be collected for MM disease specifics. Height and weight are also collected only at screening.

 Disease response to be done at discretion of physician in keeping with standard of care.

 Transplant day is day 0.

 Female of child-bearing potential must have two negative urine pregnancy test results within at time of eligibility testing and prior to GCS-F pre-transplant as a way of ensuring safe transplant planning.

Organ function measured by standard clinical care labs collected from CBC, complete metabolic panel to assess the kidney, liver function.

 Subjects will receive one dose of plerixafor, a stem cell mobilizer, followed by pheresis on the next day to collect G-PBSC graft

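### Objective 1.3 names MRD and depth of response at 3 and 6 months, but the schedule marks marrow once, at month 4, and disease response at neither time point

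*Combined protocol and SAP*

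**What the plan says.** Section 1.3 sets out a between-arm comparison of depth of response by IMWG criteria, with "analyzing minimal residual disease (MRD) status at 3 and 6 months post-transplant" for subjects close to complete response.

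The Section 7.0 table labels day +100 as month 3, day +130 as month 4 and day +180 as month 6. Three rows matter:

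- "Data collection for Disease Assessment", with its label completed on the next page as "imaging and bone marrow": one mark, at day +130.
- Disease response: baseline, day +130, day +365 and 2 years. Footnote 3 adds "Disease response to be done at discretion of physician in keeping with standard of care".
- Disease assessment from blood and urine: baseline, day +100, day +180, day +365 and 2 years.

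Section 5.2.1 bases staging on local practice and calls for "MRD staging if they are deemed to be close to CR", without naming a day. Section 5.2.2 says that "post-transplant myeloma specific therapy may not be started before the day 100 (+/-10) visit on this protocol", except after earlier progression, which takes the subject off study. Section 10.2 lists depth of response and MRD as exploratory but gives no time point and no test.

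**The concern.** A comparison at two fixed times needs data collected at those times in both arms. The table as read gives no marrow mark and no response mark at either. Its one marrow mark lies between them, after the visit from which new myeloma therapy is allowed.

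Two things are at stake. First, MRD at 3 and 6 months would rest on whichever marrows local practice happens to produce, so availability and timing could differ between subjects and between arms. Second, month 3 is the only named time point that can precede new therapy. A reading at month 4 can combine the effect of the graft with that of therapy that was not randomised. With 10 subjects per arm and MRD confined to those near complete response, a missed or confounded reading would be hard to recover in the analysis.

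**Working it through.** The plan states no figure to reproduce here; the check compares marks and windows.

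**1. Visit windows (Section 7.0, window row)**

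- Month 3: 100 ± 10 = days 90 to 110.
- Month 4: 130 ± 7 = days 123 to 137.
- Month 6: 180 ± 10 = days 170 to 190.

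The month 4 window opens 123 − 110 = 13 days after month 3 closes, and it closes 170 − 137 = 33 days before month 6 opens. It overlaps neither.

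**2. Marks after transplant, by row**

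| Row | Day +100 | Day +130 | Day +180 | Day +365 | 2 years |
|---|---|---|---|---|---|
| Imaging and marrow | – | X | – | – | – |
| Disease response | – | X | – | X | X |
| Blood and urine | X | – | X | X | X |

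Marrow is marked at 0 of the 2 time points in the objective, and so is disease response. Blood and urine data are marked at 2 of 2.

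**3. Possible exposure to new therapy before the day +130 reading**

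For a subject who starts at the day 100 visit (days 90 to 110):

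- Shortest: 123 − 110 = 13 days.
- Longest: 137 − 90 = 47 days.

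A later start shortens this interval, possibly to nothing.

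**4. How far the column positions can be trusted**

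Each of these rows has all 17 visit cells, and the blood and urine marks fall where one would expect. That does not settle the matter. The immune blood draw row in the same table also has all 17 cells, yet its last mark is at day +150, whereas the Schema, sections 5.1.2 and 5.1.13 and Appendix B say day 180. Its first mark sits under the vaccine column, whereas section 7.1 and Appendix B place that draw before vaccination. A column error, in the original table or in the text extraction, is therefore possible for the day +130 marks too.

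**5. What survives a shift**

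If the single marrow mark belongs at day +100, month 6 has no marrow. If it belongs at day +180, month 3 has none. One mark cannot serve both time points. The exposure figures in step 3, by contrast, apply only if day +130 is the intended column.

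**The case against.** The strongest reply is that these rows record standard-of-care results and do not prescribe visits. The marrow row is headed as data collection, footnote 3 leaves response to the physician, and section 5.2.1 triggers MRD by near-complete-response status. The serum and urine data that inform that status are collected at both named time points. This stands to the extent that a reader might infer from the table that no marrow or response assessment can occur at 3 or 6 months; the documents do not say that. They permit such assessments without requiring them. A fixed-time comparison still lacks a scheduled source for MRD and for the formal response call.

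A reader might also infer that response is scheduled only at day +130. It is not: baseline, day +365 and 2 years are marked as well, and the serum and urine component is covered at months 3 and 6.

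Nor does the plan show that the day +130 reading must be confounded. Section 5.2.2 sets the earliest start, not an actual start, and it applies to both arms. Any 6-month reading may follow new therapy wherever the marrow mark sits, so that part of the problem comes from section 5.2.2 together with the choice of a 6-month time point.

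Finally, the day +130 marks may be misplaced. If so, the therapy-timing argument could fall away, but the shortage of marrow marks would remain.

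**Conclusion.** The point holds as a minor inconsistency between the objective and the schedule. As read, the table schedules one marrow collection for an objective that names two time points, places it in neither window, and marks disease response at neither. Standard-of-care provisions allow the gap to be filled but do not ensure it, and section 10.2 does not repair it. If day +130 is the intended visit, the reading may come after up to 47 days of non-randomised therapy.

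This rests on two assumptions: that the column positions are as extracted, and that the flow MRD test is done on marrow, since section 5.2.1 names the method but not the specimen. The primary endpoint, the sample size and the safety monitoring are unaffected.

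**What to change.** 1. Check the day +130 marks for disease response and for imaging and marrow against the original table. Check the immune blood draw row at the same time.
2. Reconcile sections 1.3, 5.2.1, 10.2 and 7.0 so that response and marrow/MRD data collection falls at the time points the objective names, and state those time points in section 10.2.
3. One way to do this without an added procedure is to align the existing single imaging and marrow collection, and its response mark, with the day +100 visit. That gives a reading that can precede new therapy. Response at day +180 can be derived from the blood and urine data already collected there.
4. State that 6-month MRD is available only where a standard-of-care marrow exists, and that any 6-month comparison may be affected by therapy begun after the day 100 visit.

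The therapy rule in section 5.2.2 need not change. The cost is a table edit and some wording, with no extra marrow. The drawback is that 6-month MRD will be incomplete and limited to subjects whose local practice produced a marrow, so it should be reported descriptively with the number assessed in each arm.
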